PASS information

Title	A pharmacoepidemiological study of rivaroxaban use and potential adverse outcomes in routine clinical practice in the United Kingdom
Protocol version identifier	5.2
Date of last version of protocol	20 Jan 2015
EU PAS register number	Study to be registered after PRAC approval
Active substance	B01AF01 Antithrombotic agents, direct Factor Xa Inhibitors, Rivaroxaban
Medicinal product	Xarelto®
Product reference	BAY 59-7939
Procedure number	EMA/H/C/00944
Marketing authorization holder(s)	Bayer Pharma AG, D-13353 Berlin, Germany
Joint PASS	No
Research question and objectives	
To assess patterns of drug utilization and to quantify outcomes related to safety and effectiveness in new users of rivaroxaban compared with new users of standard of care in routine clinical practice in the United Kingdom.
 
To provide a description of patients who are prescribed oral rivaroxaban for the first time in comparison with those who are prescribed standard of care for the first time, and describe the characteristics of rivaroxaban use (including indication, dose and duration).
 
To determine time-trends in the characteristics of first-time use of rivaroxaban.
 
To study the occurrence of hospitalization or referral to a specialist from primary care for three bleeding events (primary safety outcomes): (a) intracranial haemorrhage, (b) gastrointestinal bleeding and (c) urogenital bleeding among users of rivaroxaban (for the treatment of deep vein thrombosis [DVT] or pulmonary embolism [PE] and prevention of recurrent DVT and PE, stroke prevention in atrial fibrillation and prevention of atherothrombotic events

	
following an acute coronary syndrome) in comparison with individuals receiving current standard of care.
 
Secondary objectives: to study the occurrence of other bleeding events leading to hospitalization, non-infective liver disease (secondary safety outcomes) and to study outcomes related to effectiveness (DVT/PE, ischaemic stroke and myocardial infarction) and deaths.

Country(-ies) of study	United Kingdom
Author	
[name] [name]
 
Spanish Centre for Pharmacoepidemiological Research (CEIFE), Madrid, Spain
 
In collaboration with the Xarelto Epidemiology PASS Programme Group.

Marketing authorization holder

Marketing authorization holder(s)	Bayer Pharma AG, D-13353 Berlin, Germany
MAH contact person	[name]

PE	Pulmonary Embolism
PRAC	Pharmacovigilance Risk Assessment Committee
REC	Research Ethics Committee
RMP	Risk Management Plan
SPAF	Stroke Prevention in Atrial Fibrillation
THIN	The Health Information Network
UK	United Kingdom
VTE	Venous thromboembolism

3 Responsible parties

Principal investigator: [name] [name]

Spanish Centre for Pharmacoepidemiological Research (CEIFE), Madrid, Spain.

Qualified Person for Pharmacovigilance: [name]

Bayer Pharma AG, D-13353 Berlin, Germany.

4 Abstract

A pharmacoepidemiological study of rivaroxaban use and potential adverse outcomes in routine clinical practice in the United Kingdom

Version 5.2, 20 Jan 2015

Principal investigator: [name] [name]

Spanish Centre for Pharmacoepidemiological Research (CEIFE), Madrid, Spain

In collaboration with the Xarelto Epidemiology PASS Programme Group.

Rationale and background

Rivaroxaban is an oral, direct Factor Xa inhibitor with multiple indications, including: treatment of deep vein thrombosis (DVT) and pulmonary embolism (PE) and prevention of recurrent DVT and PE; stroke prevention in atrial fibrillation (SPAF); and prevention of atherothrombotic events (when combined with antiplatelet therapy) following an acute coronary syndrome (ACS). The use of anticoagulants is associated with the risk of bleeding, and monitoring of the safety profile and patterns of rivaroxaban use in routine care is required. This study in the United Kingdom forms part of a post-authorization safety study programme in several European countries.

Research question and objectives

To provide a detailed description of patients who are prescribed oral rivaroxaban for the first time in comparison with those who are prescribed standard of care for the first time, and describe the characteristics of rivaroxaban use (including indication, dose and duration of treatment). To determine time-trends in the characteristics of first-time use of rivaroxaban. Primary safety outcomes are the occurrence of hospitalization or referral to a specialist for intracranial haemorrhage, gastrointestinal bleeding or urogenital bleeding, among users of rivaroxaban in comparison with individuals receiving current standard of care.

Study design

This study has a cohort design.

Population

All patients aged 2 years and above who have been enrolled in The Health Improvement Network (THIN) database for at least 1 year and had their first prescription recorded in the database at least 1 year ago will be included.

Variables

Detailed descriptive variables will be captured for the population, including co-medications and comorbidities. Primary safety outcomes are the occurrence of hospitalization for intracranial haemorrhage, gastrointestinal bleeding and urogenital bleeding. Other outcomes of interest include hospitalization for bleeding events not defined in the primary outcome (other bleeding), non-infective liver disease, outcomes related to effectiveness (DVT/PE, ischaemic stroke, myocardial infarction), and deaths.

Data sources

THIN. The population included in THIN is representative of the UK as a whole in terms of age, sex and geographic distribution.

Study size

The size of the population receiving rivaroxaban will be dependent on market uptake across the indications of interest. Based on an incidence of haemorrhagic stroke in warfarin-treated patients of 5 per 1000 person-years, 12,000 rivaroxaban-treated patient-years and 48,000 warfarin-treated patient-years would be required to exclude a 50% increased risk of haemorrhagic stroke in rivaroxaban-treated patients compared with warfarin-treated patients with a power of 80%.

Data analysis

The patient populations will be described according to the descriptive variables, overall and stratified by indication (VTE prevention, DVT/PE treatment, SPAF, ACS, other), naïve or non-naïve status, and switching status. Age- and sex-adjusted odds ratios and 95% confidence intervals for the descriptive variables, will be computed using logistic regression models both overall and stratified by indication and by naïve or non-naïve status, and switching status.

Crude incidence rates for the safety and effectiveness outcomes will be estimated in both cohorts for DVT/PE treatment, SPAF and ACS. Incidence will be computed using the person–time contribution of the study cohorts, stratified into current, recent, past and non-use.

Age- and sex-adjusted rate ratios with 95% CIs will be estimated for each of the three primary adverse outcomes comparing rivaroxaban with standard of care using Poisson regression analysis based on person–time contribution.

Milestones

Data collection will start from 09 December, 2011 (when rivaroxaban received marketing authorization for DVT treatment in the UK) and finish on 31 December, 2018.

5 Amendments and updates

Table 1: Amendments

Number	Date	Section of study protocol	Amendment	Reason
6	Jan 2015	9.3.2.1 9.7.2.5 9.7.2.6	Addition to section on bleeding definition Addition to section on renal failure definition Addition a section on how to handle missing data	Response to PRAC review
5	Nov 2014	8.2 9.3.1 9.7.1 9.7.2.5	Additional variables for patient characterisation and analyses thereof; strengthened analyses of renal impairment	Response to PRAC review
4	May 2014	General	Extension of study timelines. Comparator updated for acute coronary syndromes. Added secondary safety outcome: “other bleeding” Transfer to EMA protocol template. Label wording updated. Current protocol is V5.0.	PRAC request
3	Mar 2012		Inclusion of additional indication, treatment of pulmonary embolism. V4.0 of protocol.	Label expansion
2	Dec 2011		Inclusion of additional indication, acute coronary syndrome. V3.0 of protocol submitted with EU RMP V 7.1	Label expansion
1	Apr 2011		Inclusion of additional indication, stroke prevention	Label expansion

			in atrial fibrillation. V2.0 of protocol submitted with EU RMP V 6.1.	
--	--	--	---	--

6 Milestones

Table 2: Milestones

Milestone	Planned date
Start of data collection (Marketing Authorization granted for DVT treatment)	Q4 2011
Interim report 1 2 years drug utilization data and crude incidences for primary safety outcomes	Q4 2015
Interim report 2 4 years drug utilization data and crude incidences for primary safety outcomes	Q4 2017
End of data collection	Q4 2018
Final data availability	Q4 2019
Progress reports	Annual in November 2014–19
Final report of study results with full outcomes analysis	Q4 2020
Registration in the EU PAS register	Study to be registered after PRAC approval

7 Rationale and background

Rivaroxaban, a direct Factor Xa inhibitor, is licensed for multiple indications:

- The treatment of deep vein thrombosis (DVT) or pulmonary embolism (PE), and prevention of recurrent DVT and PE in adult patients (DVT/PE treatment) (15 mg rivaroxaban twice daily [bid] for 3 weeks, then 15 mg or 20 mg once daily [od]).
- The prevention of stroke and systemic embolism in adult patients with non-valvular atrial fibrillation (stroke prevention in atrial fibrillation [SPAF]) with one or more risk factors, such as congestive heart failure, hypertension, age \geq 75 years, diabetes mellitus, prior stroke or transient ischaemic attack (20 mg rivaroxaban od).
- The prevention of venous thromboembolism (VTE) in adult patients undergoing elective hip or knee replacement surgery (recommended dose: 10 mg rivaroxaban od for 35 days following hip replacement surgery and 14 days following knee replacement surgery).
- Co-administered with acetylsalicylic acid (ASA) alone or with ASA plus clopidogrel or ticlopidine, for the prevention of atherothrombotic events in adult patients after an acute coronary syndrome (ACS) with elevated cardiac biomarkers (recommended dose 2.5 mg bid).

As is the case with other anticoagulants, clinical studies of rivaroxaban have identified haemorrhage as an important safety outcome ([Lassen, Ageno et al. 2008](#); [Turpie, Lassen et al. 2009](#)). A post-authorization safety study programme is planned for several European countries. This document summarizes the design of a population-based study to characterize new users of rivaroxaban, assess patterns of drug utilization, including adherence to label recommendations, and to assess the risk of bleeding associated with rivaroxaban treatment compared with the standard of care in routine clinical practice in the UK, for ACS, DVT/PE treatment and SPAF. For DVT/PE treatment and SPAF, standard of care is treatment with the most widely used vitamin K antagonist, warfarin, and for the secondary prevention of ACS, standard of care is antiplatelet drug(s) such as low-dose acetylsalicylic acid, clopidogrel, dipyridamole, prasugrel, ticlopidine and ticagrelor.

8 Research questions and objectives

This post-authorization study was designed to assess patterns of drug utilization and to quantify outcomes related to safety and effectiveness in new users of rivaroxaban compared with new users of standard of care.

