9.1 Study design

This study has a cohort design including nested case–control analyses.

Cohorts of first-time users of either rivaroxaban or comparators will be identified using the date of first prescription (index date) of the respective drug (index drug) (Figure 1).

A patient will be considered eligible to enter the study cohort as a first-time user of rivaroxaban or a first-time user of “standard of care” when he or she has a first prescription of the drug recorded during the enrolment period. In the UK, for VTE prevention, DVT/PE treatment and SPAF, standard of care is treatment with the most widely used vitamin K antagonist, warfarin, and for the secondary prevention of ACS, standard of care is antiplatelet drug(s) such as low-dose acetylsalicylic acid, clopidogrel, dipyridamole, prasugrel, ticlopidine and ticagrelor.

Patients who have any record of being prescribed their index drug prior to the enrolment period or who qualify as members of both cohorts on the same day, will be excluded. If a patient qualifies as first-time user of both rivaroxaban and “standard of care” comparison drug during the enrolment period, she/he will be assigned to the cohort of drug first prescribed during the enrolment period, with the date of this prescription being the index date.

Many patients with ACS have a history of ischaemic heart disease for which platelet inhibition is standard treatment, and thus exclusion of patients with prior use of platelet inhibitors risks excluding a majority of typical ACS patients. Therefore, those who have been using one or more platelet inhibitors will remain eligible to enter the study.

Standard of care for ACS patients is combination therapy, and as such cohort assignment will be based on first use of rivaroxaban (in combination with aspirin or clopidogrel, or multi-antiplatelet therapy), or use of aspirin and clopidogrel and/or other antiplatelet medications.

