9.2 Setting

All patients aged 2 years and above who have been enrolled with a primary care physician for at least 1 year and had their first prescription recorded in the database at least 1 year ago will be included.

The population included in THIN is representative of the UK as a whole in terms of age, sex and geographic distribution ([Bourke, Dattani et al. 2004](#); [Blak, Thompson et al. 2011](#)). THIN has been extensively validated for use in pharmacoepidemiology ([Lewis, Schinnar et al. 2007](#)), and has been used successfully in studies of bleeding risk ([Tata, Fortun et al. 2005](#); [Smeeth, Cook et al. 2006](#); [García Rodríguez and Barreales Tolosa 2007](#); [de Abajo and Garcia-Rodriguez 2008](#); [Massó González and García Rodríguez 2008](#); [Raine, Wong et al. 2009](#); [Cea Soriano and García Rodríguez 2010](#); [Gaist, Wallander et al. 2013](#); [Garcia-Rodriguez, Gaist et al. 2013](#)).

The enrolment period will start on the day after rivaroxaban receives first marketing authorization for the ‘treatment of DVT and long-term secondary prevention of recurrent DVT and PE’. End of enrolment will be 31 December 2017 and end of follow-up will be 31 December 2018. Interim reports will be provided for data collected 2 and 4 years after the date that rivaroxaban receives NICE approval for DVT treatment (see [Section 6](#) for detailed milestones).

To study outcomes of interest ([Section 8](#)) for patients receiving rivaroxaban and comparators for DVT/PE treatment, SPAF or ACS, the same source population will be used as in the drug utilization study.

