- comorbidity based on diagnoses most recently recorded before the index date and in following the index date, such as haemorrhagic disease, liver disease, pancreatic disease, cancer (including the presence of malignant neoplasm), cardiovascular disease, cardiovascular risk factors (hypertension, diabetes mellitus, hyperlipidaemia and obesity), peripheral arterial disease, respiratory disease (asthma and chronic obstructive pulmonary disease), rheumatoid arthritis, osteoarthritis, gastrointestinal disease (recent gastrointestinal ulceration [including peptic ulcer disease], gastritis and duodenitis, dyspepsia and gastroesophageal reflux disease), oesophageal varices, arteriovenous malformations, vascular aneurysms or major intraspinal or intracerebral vascular abnormalities, thyroid disease, surgical procedures (including PCI, CABG, and recent brain, ophthalmic or spinal surgery, where recorded), presence of a prosthetic heart valve (if recorded), alcohol-related disorders, ventricular arrhythmia, anaemia, and history of intracranial haemorrhage, urogenital bleeding and gastrointestinal bleeding; if possible, a CHADS score will be calculated based on the presence of congestive heart failure, hypertension, age, diabetes mellitus and prior stroke or transient ischaemic attack; also, where possible, a HAS-BLED score for major bleeding risk (hypertension, renal disease, liver disease, stroke history, prior major bleeding or predisposition to bleeding, age > 65, medication usage predisposing to bleeding, alcohol usage history, labile INR [if available]) will be calculated; ✓
- smoking status, body mass index (BMI) and Townsend score: most recently recorded before the index date and following the index date;
- healthcare utilization in the year prior to the index date (e.g. PCP visits, outpatient visits and hospital admissions). ✓

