9.4 Data sources

The data source for this study will be The Health Improvement Network (THIN) database in the UK. THIN includes information on over 3 million patients (approximately 5% of the UK population) that is systematically recorded by participating PCPs as part of their routine patient care and is anonymized and sent to THIN for use in research projects. The computerized information includes demographics, details of PCP visits, referrals to specialists and hospital admissions (including diagnostic and treatment information), results of laboratory tests and a free-text section. Prescriptions issued by the PCP are recorded electronically and the indication can be ascertained by reviewing the patient's clinical history. The Read classification is used to code specific diagnoses as reasons for each consultation (O'Neil, Payne et al. 1995; Stuart-Buttle, Read et al. 1996), and a drug dictionary based on data from the MULTILEX classification is used to record prescriptions (First Data Bank 2014).

Recently, a number of practices included in THIN database have been linked to the HES database. HES is a data warehouse containing details of all admissions, outpatient appointments and Accident and Emergency attendances at NHS hospitals in England.

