9.7.2.1 Primary safety outcomes

Crude incidence rates will be estimated for each of the three primary adverse outcomes in both cohorts. Age- and sex-adjusted rate ratios with 95% CIs will be estimated for each of the three primary adverse outcomes comparing rivaroxaban with standard of care using Poisson regression analysis based on person–time contribution (current, recent and past use as defined in [Section 9.7.2](#)).

Where numbers and data permit, adjustment will be made for baseline medication and comorbidity variables described in the drug utilization section, including indication and history of adverse outcomes (referral or hospitalization for haemorrhagic stroke, gastrointestinal bleeding or urogenital bleeding recorded at any time before the index date).

If numbers of final cases permit, estimation of the relative risk among rivaroxaban users will be adjusted for known risk factors of the specific outcome using logistic regression models in nested case-control analyses.

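### The protocol introduces SPAF as non-valvular AF, but no rule keeps warfarin users with a prosthetic valve or valvular AF out of the SPAF comparator

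*Protocol*

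**What the plan says.** - **Indication.** Section 7 attaches the label SPAF to a non-valvular population: "The prevention of stroke and systemic embolism in adult patients with non-valvular atrial fibrillation (stroke prevention in atrial fibrillation [SPAF"]). The abbreviation list expands SPAF as stroke prevention in atrial fibrillation, with no valve qualifier, and the objectives add none.
- **Comparator.** Section 7: "For DVT/PE treatment and SPAF, standard of care is treatment with the most widely used vitamin K antagonist, warfarin". No valve restriction is attached.
- **Entry.** Section 9.2 takes "All patients aged 2 years and above who have been enrolled with a primary care physician for at least 1 year". Section 9.1 makes a patient eligible "when he or she has a first prescription of the drug recorded during the enrolment period". Its exclusions concern only prior drug use and same-day dual membership: "Patients who have any record of being prescribed their index drug prior to the enrolment period or who qualify as members of both cohorts".
- **Indication assignment.** Section 9.3.1 collects the diagnosis linked to the index prescription. Section 9.4 says that "the indication can be ascertained by reviewing the patient's clinical history". Section 9.7.1 lists five strata: VTE prevention, DVT/PE treatment, SPAF, ACS and *other*. Sections 9.2 and 9.7.2 confine the outcome work to DVT/PE treatment, SPAF and ACS.
- **Valve information.** Section 9.3.1 lists, among comorbidities, "presence of a prosthetic heart valve (if recorded"). Valvular AF and native valve disease are not named.
- **Adjustment.** Section 9.7.2.1 commits to age- and sex-adjusted rate ratios. Beyond that: "Where numbers and data permit, adjustment will be made for baseline medication and comorbidity variables described in the drug utilization section".

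**The concern.** The rivaroxaban SPAF indication is stated as non-valvular, while the warfarin group it is compared with is not limited in the same way. A warfarin patient with AF and a valve prosthesis meets every written entry criterion, and the reason for prescribing could reasonably be read as stroke prevention in AF. The same patient lies outside the rivaroxaban indication that the protocol quotes. If such patients are counted, they may sit almost entirely in one cohort, which is a lack of overlap that age and sex adjustment does not address.

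At stake is whether the SPAF rate ratio describes the stated indication. If these patients have a different event rate, the warfarin rate is shifted for a reason unrelated to the drugs. The two interim reports give crude incidences of the primary safety outcomes (Section 6), so no adjustment is promised there.

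**Working it through.** **1. Can the text settle where a valvular AF patient on warfarin goes?**

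| Step | What the protocol provides | Keeps the patient out of SPAF? |
|---|---|---|
| Entry (9.1, 9.2) | age, registration time, first prescription, no earlier index drug, no same-day dual entry | No |
| Indication (9.3.1, 9.4) | diagnosis linked to prescribing, from clinical history | No valve rule given |
| Strata (9.7.1) | SPAF and *other* both exist | Possible, but no rule assigns the patient |
| Codes (Annex 3) | outcome Read codes only | No |
| Adjustment (9.7.2.1) | age and sex firm; prosthetic valve conditional | No |

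The Section 7 definition allows the patient to be placed in *other*. The unqualified use of SPAF elsewhere allows placement in SPAF. Neither is excluded.

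**2. Size of the effect if they are counted in SPAF.** Let r be the bleeding rate in non-valvular warfarin users, p the valvular share of warfarin SPAF person-time, and k their rate relative to r after age and sex adjustment. Both p and k are assumptions, taken as constant across age-sex groups.

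Warfarin rate = r(1−p) + rkp = r[1+p(k−1)].

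With no such patients under rivaroxaban, observed ratio = true ratio / [1+p(k−1)].

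| p | k | Divisor | True 1.00 reads | True 1.50 reads |
|---|---|---|---|---|
| any | 1 | 1.000 | 1.00 | 1.50 |
| 5% | 1.5 | 1.025 | 0.976 | 1.463 |
| 10% | 1.5 | 1.050 | 0.952 | 1.429 |
| 10% | 2 | 1.100 | 0.909 | 1.364 |

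If the rivaroxaban cohort also has a share q with the same k, the ratio is multiplied by [1+q(k−1)]/[1+p(k−1)], which is 1 when q=p.

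**3. The plan's own study size (Section 9.5), and the cost of restriction.** Inputs: 5 haemorrhagic strokes per 1000 warfarin person-years, 12,000 and 48,000 patient-years, exclusion of a ratio of 1.5. Alpha is not stated; two-sided 0.05 is assumed.

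- Expected events at a true ratio of 1: 12,000×0.005 = 60 and 48,000×0.005 = 240.
- SE of the log ratio = √(1/60+1/240) = 0.1443.
- Power = Φ(ln 1.5/0.1443 − 1.96) = Φ(0.849) = 80.2%. The stated 80% reproduces.
- Remove 5% of warfarin person-time: 228 events, SE 0.1451, power 79.8%.
- Remove 10%: 216 events, SE 0.1459, power 79.3%.

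**4. Chance of wrongly excluding 1.5 when it is true.** As an upper illustration, apply p to all 48,000 warfarin patient-years, with 60×1.5 = 90 rivaroxaban events.

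- p=5%, k=1.5: warfarin events 240×1.025 = 246, SE = √(1/90+1/246) = 0.1232, Φ(ln 1.025/0.1232 − 1.96) = 3.9%.
- p=10%, k=2: warfarin events 240×1.10 = 264, SE = 0.1221, Φ(ln 1.10/0.1221 − 1.96) = 11.9%.
- The nominal figure is 2.5%. Section 9.5 does not limit its warfarin person-time to SPAF, so p in a pooled analysis would be smaller.

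**The case against.** The strongest reply is that broad entry and indication assignment are separate steps. Entry is wide because the study also describes drug use and label adherence. SPAF membership is decided later, Section 7 ties SPAF to non-valvular AF, and a valve patient would then fall into *other* and leave the outcome comparison. This reading is available and cannot be ruled out. A reader might infer that the warfarin SPAF group definitely contains valve patients; the protocol does not show that. It shows only that nothing prevents it.

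A second reply is that code lists and indication algorithms commonly belong in the analysis plan, which is not at hand. That stands for the codes. Who belongs in a comparison cohort is protocol content, and here the indication text and the eligibility text do not match.

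Third, some handling exists. Prosthetic valve is a collected covariate. If it is adjusted for, a stratum found only under warfarin adds little to the drug contrast. Section 9.7.2.1 also offers nested case-control analyses, and Section 9.7.2.7 promises to account for unexpected biases. These are real but conditional or general. The covariate depends on recording, and native-valve AF has no named variable; the comorbidity list is open-ended, but a broad cardiovascular category would not isolate it.

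Finally, p, k and the absence of such patients under rivaroxaban are all assumed. Off-label rivaroxaban use is something the study sets out to observe, so q may not be zero.

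**Conclusion.** The point holds as a gap in the definition of the SPAF comparison population: the protocol states a non-valvular indication and does not carry it into eligibility, indication assignment or the firm part of the analysis.

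Its size is conditional. Under the assumed values a true ratio of 1.00 reads between 0.98 (p=5%, k=1.5) and 0.91 (p=10%, k=2). The first shift is small beside the 1.5 margin in Section 9.5; the second is not negligible. A reader might conclude that the bias favours rivaroxaban. The documents do not support that as a flat statement: on bleeding it is so only if k>1 and the valvular share is larger under warfarin. There is none at k=1, and it reverses if k<1. The stated study size is unaffected. The change is worth making because it is cheap and removes the ambiguity whatever p and k turn out to be.

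**What to change.** In Sections 9.1/9.2 and 9.7.2, define the SPAF outcome comparison as non-valvular AF in both cohorts. Exclude from it any patient with a prosthetic valve, mitral stenosis or other valvular-AF code on or before the index date. State that these patients are classified under *other*. Keep them in the drug-utilization and label-adherence description, and report the number removed from each cohort.

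The cost is a few sentences and a short code list; prosthetic valve is already collected. Some warfarin person-time is lost: on the Section 9.5 figures, removing 5 to 10% leaves power at 79.8 to 79.3%, against 80.2%. Valve disease that is not recorded in primary care will remain in both groups, and the report should say so.
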